9.4. Reporting of Serious Adverse Events

Regardless of suspected causality (eg, relationship to study treatment or study procedures), all SAEs occurring after the participant has signed the ICF through at least 90 days after the last dose of study treatment, regardless of the start of a new anticancer therapy, must be reported to the sponsor (or designee) within 24 hours of learning of its occurrence unless otherwise specified by the Protocol. The investigator will submit any updated SAE data to the sponsor (or designee) within 24 hours of it being available.

Investigators are not obligated to actively seek SAE information after the safety follow-up visit or 90 days after the last dose of study treatment. If the investigator learns of any SAE, including a death, at any time during the disease status follow-up or survival status follow-up period, and he/she considers the event to be reasonably related to the study treatment or study participation, the investigator must notify the sponsor (or designee) within 24 hours of becoming aware of the event.

After the initial AE/SAE report, the investigator is required to proactively follow each participant at subsequent visits/contacts. All SAEs and irAEs (as defined in Section 6.5.3) will be followed until resolution, stabilization, the event is otherwise explained, or the participant is lost to follow-up (as defined in Section 7.3).

Prompt notification by the investigator to the sponsor regarding an SAE is essential so that legal obligations and ethical responsibilities toward the safety of participants and the safety of a study treatment under clinical investigation are met.

If the SAE is not documented in the RSI of the IB for any of the study drugs (new occurrence; refer to [retifanlimab IB](#), [INCAGN02385 IB](#), and [INCAGN02390 IB](#)) and is thought to be related to the study treatment, the sponsor or its designee may urgently require further information from the investigator for expedited reporting to health authorities. The sponsor or its designee may need to issue an Investigator Notification to inform all investigators involved in any study with

the same drug that this SAE has been reported. Suspected unexpected serious adverse reactions will be collected and reported to the competent authorities and relevant ethics committees in accordance with Directive 2001/20/EC, EU CTR No. 536/2014, and FDA 21 CFR Part 312 or as per national regulatory requirements in participating countries.

The sponsor has a legal responsibility to notify both the local regulatory authority and other regulatory agencies about the safety of a study treatment under clinical investigation. The sponsor will comply with country-specific regulatory requirements relating to safety reporting to the regulatory authority, IRB/IEC, and investigators.

Investigator safety reports must be prepared for suspected unexpected serious adverse reactions according to local regulatory requirements and sponsor policy and forwarded to investigators as necessary.

An investigator who receives an investigator safety report describing an SAE or other specific safety information (eg, summary or listing of SAEs) from the sponsor will review and then file it along with the IB and will notify the IRB/IEC, if appropriate, according to local requirements.

Serious Adverse Event Reporting

- Information about all SAEs is collected and recorded on the Adverse Event Form in the eCRF.
- The investigator must report within 24 hours of learning of its occurrence any SAE via the EDC system (primary method) or by completing the Serious Adverse Event Report Form in English (only if the EDC system is not available. The contact information for Incyte Pharmacovigilance by email/fax is listed in the Study Reference Manual or as per the Incyte Reference Guide for Completing the Serious Adverse Event Report Form).
- In circumstances where the EDC system is not accessible for reporting SAE information (initial and/or follow-up SAE information) to the sponsor within 24 hours, refer to the Incyte Reference Guide for Completing the Serious Adverse Report Form. Once the EDC system is functional, the SAE report should be retrospectively added to the EDC system and follow-up should be completed through the EDC. The original copy of the Serious Adverse Event Report Form and the email or facsimile confirmation sheet must be kept at the study site (refer to the Incyte Reference Guide for Completing the Serious Adverse Report Form or Study Reference Manual for details and for the email address or fax number).
- Follow-up information is also recorded in the eCRF and transmitted to Incyte Pharmacovigilance via the EDC system. The follow-up report should include information that was not provided previously, such as the outcome of the event, treatment provided, action taken with study treatment because of the SAE (eg, dose reduced, interrupted, or discontinued), or participant disposition (eg, continued or withdrew from study participation). Each recurrence, complication, or progression of the original event should be reported as follow-up to that event, regardless of when it occurs.

9.5. Events of Clinical Interest

No specific AEs are expected to be sent to the sponsor within an expedited manner aside from the AEs that meet the seriousness category as described in Section 9.4.

Immune-related AEs will be identified by investigator assessment as well as using sponsor-predefined preferred terms based on the ICI class regardless of investigator's assessment of causality. Both investigator assessed and sponsor-assessed irAEs will be summarized.

9.6. Emergency Unblinding of Treatment Assignment

In a medical emergency, if knowledge of the treatment assignment is necessary to determine optimal medical management of the participant, the procedure for emergency unblinding is provided in the IRT Manual. This option may be used *only* if the participant's well-being requires the investigator to be aware of the participant's treatment assignment. If a participant's treatment assignment is unblinded, the sponsor or its designee must be notified immediately by telephone.

If an investigator, the site personnel performing assessments, or a participant is unblinded, then the participant must discontinue study treatment unless there are ethical reasons to have the participant remain on the study treatment. In these cases, the investigator must obtain specific approval from the sponsor's (or its designee's) medical monitor for the participant to continue in the study.

9.7. Pregnancy

Pregnancy, in and of itself, is not regarded as an AE unless there is suspicion that the study treatment may have interfered with the effectiveness of a contraceptive medication or method. When a pregnancy has been confirmed in a participant during maternal or paternal exposure to study treatment, the following procedures should be followed in order to ensure safety:

- The study treatment must be interrupted immediately (female participants only).
- If the female participant is no longer pregnant and meets the treatment continuation criteria within 28 days of the scheduled start of a cycle, study treatment may be resumed after approval has been received from the sponsor's medical monitor.
- The investigator must complete and submit the Incyte Clinical Trial Pregnancy Form to the sponsor or its designee within **24 hours** of learning of the pregnancy.

Data on fetal outcome are collected for regulatory reporting and drug safety evaluation. Follow-up should be conducted for each pregnancy to determine outcome, including spontaneous or voluntary termination, details of the birth, and the presence or absence of any birth defects, congenital abnormalities, or maternal and/or newborn complications, by following until the first well-baby visit. Pregnancy should be recorded on a Clinical Trial Pregnancy Form and reported by the investigator to the sponsor or its designee. Pregnancy follow-up information should be recorded on the same form and should include an assessment of the possible causal relationship to the sponsor's study drug to any pregnancy outcome, as well as follow-up to the first well-baby visit or the duration specified in local regulations, whichever is later. Refer to the Incyte Reference Guide for Completing the Clinical Trial Pregnancy Form.

Any SAE occurring during pregnancy of a study participant must be recorded on the Serious Adverse Event Report Form and submitted to the sponsor or its designee.

Abnormal pregnancy outcomes (eg, spontaneous abortion, fetal death, stillbirth, congenital anomalies, or ectopic pregnancy) are considered SAEs (if occurring in the study participant) and must be reported as described in Section 9.4. If an abnormal pregnancy outcome is reported in a study participant's partner, the event should be reported to the sponsor on the Clinical Trial Pregnancy Form.

9.8. Warnings and Precautions

Special warnings or precautions for the study treatment, derived from safety information collected by the sponsor or its designee, are presented in the IBs. Additional safety information collected between IB updates will be communicated in the form of Investigator Notifications. Any important new safety information should be discussed with the participant during the study as necessary. If new significant risks are identified, they will be added to the ICF.

9.9. Product Complaints

The sponsor collects product complaints on study drugs and drug delivery systems used in clinical studies in order to ensure the safety of study participants, monitor quality, and facilitate process and product improvements.

All product complaints associated with material packaged, labeled, and released by the sponsor or its designee will be reported to the sponsor. All product complaints associated with other study material will be reported directly to the respective manufacturer.

The investigator or his/her designee is responsible for reporting a complete description of the product complaint via email or other written communication to the sponsor contact or respective manufacturer as noted in the packaging information. Any AE associated with a product complaint should be recorded as described in Section 9.3.

If the investigator is asked to return the product for investigation, he/she will return a copy of the product complaint communication with the product.

9.10. Treatment of Overdose

For retifanlimab, a dose > 1500 mg within a 24-hour time period will be considered an overdose. In the event of an overdose of retifanlimab, the following should occur:

- Appropriate supportive treatment should be provided if clinically indicated.
- The investigator should contact the medical monitor immediately and closely monitor the participant for any AEs/SAEs and laboratory abnormalities per Section 9.3.
- The quantity of the excess dose as well as the duration of the overdose should be documented in the eCRF.

Decisions regarding dose interruptions will be made by the investigator in consultation with the medical monitor based on the clinical evaluation of the participant.

There has been no clinical experience with overdose of INCAGN02385 or INCAGN02390. Treatment of overdose should consist of general supportive measures.

10. STATISTICS

This section outlines the statistical analysis strategy and procedures for this study. If changes are made to primary efficacy and safety and/or secondary efficacy hypotheses or the statistical methods related to those hypotheses after the study has begun, but before the final database lock, the Protocol will be amended, consistent with ICH E9 (1998) and ICH E9 (R1; 2021). The detailed statistical analyses will be documented in the Statistical Analysis Plan.

10.1. Sample Size Determination

The sample size calculation is based on the primary endpoint of PFS. Approximately 162 participants will be randomized in a 1:1:1 ratio into TG1:TG2:TG3. The study is event-driven and will be complete after approximately 94 PFS events have been observed between TG1 and TG2 or between TG1 and TG3 (approximately 140 PFS events across the 3 treatment groups). Based on a target of 94 PFS events for all participants at the final analysis between TG1 and TG2 or between TG1 and TG3 (approximately 140 PFS events across the 3 treatment groups), which is expected to occur about 20 months from the start of enrollment, the study has approximately 80% power to detect an HR of 0.6 at an overall alpha level of 5% (1-sided) favoring one of the combination therapies with the assumption of study parameters as specified in Table 17 for PFS.

The sample size and power calculations were performed in R package "gsDesign."

Table 17: Sample Size Assumptions for Progression-Free Survival

Variable	Assumptions
Median PFS in TG1 (All participants)	3 months ^a
Randomization ratio	1:1:1
Assumed HR (All participants)	0.6
Enrollment duration	12 months
Follow-up for PFS	8 months
Assumed annual dropout rate	1%

^a Burtneess et al 2019.

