10.3. Level of Significance

For the primary endpoint, the overall 1-sided alpha level will be strongly controlled 10%, with an initial 1-sided alpha allocation for each hypothesis at 5% (refer to SAP). The detailed multiplicity control will be specified in the Protocol Section 10.6. Unless otherwise stated, all CIs provided will be reported at a 95% confidence level.

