PD or death documented after ≥ 2 missed disease assessments	Censored at last disease assessment prior to the ≥ 2 missed disease assessment	Progressed at date of documented PD or death	Progressed at date of documented PD or death

The stratified log-rank test will be used to compare PFS between treatment groups in the ITT at a 1-sided 5% significance level, stratified for LAG-3 expression status ($\geq 5\%$ vs $< 5\%$), PD-L1 CPS (1%-19% vs $\geq 20\%$), and HPV p16 status (p16-positive vs p16-negative, oropharyngeal only). The strata identified in the randomization process will be used for the analysis.

The HR and its 95% CI will be estimated based on the stratified Cox regression model using the same stratification factors as for the log-rank test with Efron's method accounting for ties in event times (1977).

Kaplan-Meier curves for PFS will be presented by treatment groups. The Kaplan-Meier estimate of median PFS will be presented with its 95% CI. The 95% CI will be calculated using the generalization of Brookmeyer and Crowley's method (1982) with log-log transformation (Klein and Moeschberger 1997).

Since disease progression is assessed periodically, PD can occur any time in the time interval between the last assessment at which PD was not documented and the assessment when PD is documented. In order to evaluate the robustness of the PFS endpoint per RECIST v1.1 based on investigator review, 2 sensitivity analyses with a different set of censoring rules will be performed. For the first sensitivity analysis, participants who miss more than 1 disease assessment are not handled differently from participants who miss 0 or 1 disease assessment (ie, the status depends on if there is PD or death).

The second sensitivity analysis handles participants who discontinue treatment or initiate an anticancer treatment subsequent to discontinuation of study-specified treatments differently from the primary analysis. The censoring rules for these 2 sensitivity analyses are also summarized in Table 20. Within each analysis, if a participant meets multiple criteria for censoring, the censoring criterion that occurs earliest will be applied.

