3.2. Sample Size Considerations and Timing of Final Analysis

The sample size calculation is based on the primary endpoint of PFS. Approximately 162 participants will be randomized in a 1:1:1 ratio into TG1:TG2:TG3.

The final analysis will be performed after approximately 94 PFS events have been observed between TG1 and TG2 or between TG1 and TG3 (approximately 140 PFS events across the 3 treatment groups) or the last participant has been followed up for at least 8 months after randomization, whichever is earlier.

The sample size and power calculations were performed in R package "gsDesign" and as tabulated in [Table 2](#).

Table 2: Boundary Properties for Final Analysis of Progression-Free Survival Based on Potential Alpha Levels

Analysis	Value	$\alpha = 0.05$ (1-Sided)	$\alpha = 0.10$ (1-Sided)
Final	Z	1.645	1.2816
N: 108	p (1-sided)	0.0500	0.1000
Events: 94 (approximately 140 events across 3 treatment groups)	~HR at bound	0.7120	0.7670
Month: 20	P (Cross) if HR = 1	0.0500	0.1000
	P (Cross) if HR = 0.6	0.8000	0.8840

Based on a target of 94 PFS events for all participants at the final analysis between TG1 and TG2, which is expected to occur about 20 months from the start of enrollment if 108 participants are enrolled within 12 months, the study has approximately 80% power to detect an HR of 0.6 at an alpha level of 5% (1-sided), favoring a combination therapy versus TG1 with the assumption of study parameters as specified in Table 17 of the Protocol. When the 1-sided alpha level is 10%, the statistical power is 88.4%. The same assumption and sample size calculation approach is followed for TG3 and TG1.

The total sample size across the 3 treatment groups is calculated using 1.5 times the sample size from 2 treatment groups.

In case of delay in achieving the targeted number of PFS events, the primary analysis may be conducted when the last participant has been followed up for at least 8 months after randomization, even if the targeted number of events is not reached. In this case, the median PFS follow-up time across the blinded treatment groups will be quantified using the reverse Kaplan-Meier method and monitored by the study team. The study team will evaluate if the lower limit of the 95% CI for the median PFS follow-up time is achieved after 8 months.

[Table 3](#) shows the boundary properties for scenarios when the number of PFS events is approximately 108, 123, and 130 across the 3 treatment groups.

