10.1. Changes to Protocol-Defined Analyses

The following changes were made in the original SAP:

- Clarification was provided to depict that the overall alpha level is strongly controlled at 10% (1 sided). Furthermore, it was clarified that the alpha level of 5% is used when comparing one combination therapy versus TG1.
- The number of PFS events was updated to 94 (see [Table 2](#)) and the approximate number of PFS events (140) across 3 treatment groups was added.
- The ADA evaluable population was added.
- The censoring rule for PFS was updated to align the situations with the primary analysis algorithm-based on FDA guidelines. A sensitivity analysis, which applied alternative censoring rules for PFS, is no longer needed.
- The classification variable, "Region (North America, EU, or Asia)," was added for subgroup analysis.

The following updates were made for SAP Amendment 1:

- Added boundary properties for scenarios when the number of PFS events is approximately 108, 123, and 130 across the 3 treatment groups if the primary analysis is conducted after the last participant has been followed up for at least 8 months after randomization.
- Added analysis of the difference in ORR and DCR between TG2 and TG1 and between TG3 and TG1.
- Updated the OS analysis to only provide estimates of median OS, its 95% CI, median follow-up time for OS, and HR. The number of OS events at the final analysis does not support a valid comparison between treatment groups, and the study is not powered for OS comparison. No formal statistical testing will be conducted.

The following updates were made for SAP Amendment 2:

- Updated ORR and DCR analysis to show only the differences in ORR or DCR between treatment groups and the corresponding 95% CIs. Odds ratio and 95% CI will not be provided, as the difference is more easily interpretable.

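### Protocol 10.1 attaches its 80% power to an overall one-sided alpha of 5%, but that power belongs to one-sided 5% for each comparison with TG1; the overall level in Protocol 10.3 is 10%, and the current SAP no longer controls it.

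*Protocol*

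**What the plan says.** **Protocol.** Section 10.1 gives the design as "approximately 80% power to detect an HR of 0.6 at an overall alpha level of 5% (1-sided"), based on 94 PFS events in a pair of groups (TG1 with TG2, or TG1 with TG3). Table 19 lists two primary hypotheses: TG3 against TG1 and TG2 against TG1. Section 10.3 says "the overall 1-sided alpha level will be strongly controlled 10%, with an initial 1-sided alpha allocation for each hypothesis at 5" per cent. Section 10.4.1 uses the stratified log-rank test to "compare PFS between treatment groups in the ITT at a 1-sided 5% significance level". Section 10.6 promises strong type I error control by a graphical procedure with alpha reallocation.

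**SAP.** Section 3.2 repeats the power statement without the word *overall*: "the study has approximately 80% power to detect an HR of 0.6 at an alpha level of 5% (1-sided), favoring a combination therapy versus TG1". It adds: "When the 1-sided alpha level is 10%, the statistical power is 88.4" per cent. Table 2 puts both figures against one pair (N 108, 94 events). Section 10.1, in its list of changes made in the original SAP, records that "the overall alpha level is strongly controlled at 10% (1 sided") and that 5% is the level for one combination against TG1. Section 10.2 then records that SAP Amendment 1 removed type I error control, on the ground that it served only the sample size calculation. Section 7.3.2 accordingly reports a nominal one-sided p-value.

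**The concern.** Protocol 10.1 and 10.3 are both current text. Both use *overall* for the alpha of the primary PFS analysis, and the two values differ by a factor of two. With two hypotheses, the overall and per-comparison levels are different quantities, so at most one section can be right.

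What is at stake is a stated design property. Taken alone, 10.1 says that the chance of any false PFS finding is held at 5% while each comparison keeps 80% power. The trial does not have that combination of properties.

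**Working it through.** **Inputs.** 94 events per pair, hazard ratio 0.6, one-sided testing and 1:1:1 allocation, hence 1:1 within a pair (Protocol 10.1 and Table 17). Two hypotheses (Protocol Table 19). N = 108 per pair (SAP Table 2).

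**Step 1: reproduce the plan's power.** By Schoenfeld's approximation with 1:1 allocation, the expected value of the test statistic is

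drift = (√94 / 2) × ln(1/0.6) = 4.848 × 0.5108 = 2.476,

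and power = Φ(drift − z).

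| One-sided alpha on one comparison | z | Power | Plan's figure |
|---|---|---|---|
| 5% | 1.645 | Φ(0.831) = 79.7% | 80% (Protocol 10.1; SAP Table 2) |
| 10% | 1.282 | Φ(1.195) = 88.4% | 88.4% (SAP 3.2) |

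A Lachin–Foulkes-type calculation from Table 17 (control median 3 months, 12 months of enrolment plus 8 of follow-up, 1% annual dropout, N = 108) gives 80.8% with about 96 expected events. Freedman's formula gives 78.2%. All of these spend the full 5% on one pair.

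**Step 2: overall error when each pair is tested at 5%.** With equal groups and a shared control, each treatment difference has variance 2σ²/n, and the two differences share σ²/n through TG1. Their correlation is therefore 0.5. If neither combination works,

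familywise error = 1 − P(Z₁ < 1.645, Z₂ < 1.645; correlation 0.5) = 8.8%.

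The Bonferroni bound is 5% + 5% = 10%. Reallocation acts only after a rejection, so it does not change the 8.8%. The result agrees with the 10% in Protocol 10.3 and not with the 5% in 10.1.

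**Step 3: illustration of an overall 5%.** No document says how an overall 5% would be divided, so this is a range under stated assumptions.

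| Rule at overall one-sided 5% | Power per comparison, 94 events |
|---|---|
| 2.5% each, no reallocation | Φ(2.476 − 1.960) = 69.7% |
| Dunnett bound, z = 1.916 | Φ(2.476 − 1.916) = 71.2% |
| 2.5% each, full reallocation, both hazard ratios 0.6 | 75.5% |
| The same, only one combination effective | about 70% |

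None of these reaches 80%, so 10.1 cannot be rescued by supposing that a 5% familywise rule was meant for per-comparison power.

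**The case against.** The strongest reply is that one word is misplaced and nothing in the design depends on it. Power, hazard ratio, events and N all reproduce. Protocol 10.3 and 10.4.1 and SAP 3.2 state the per-comparison rule correctly, and 10.3 comes only two subsections after 10.1. Protocol 10.4.2.4 also uses *overall* loosely, for the alpha of a comparison of two groups in the OS analysis. All of this stands. It makes the point an inconsistency in wording, not an error in the sample size calculation, but it does not make 10.1 and 10.3 agree.

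A second reply is that power might mean success on at least one comparison. At 2.5% each, that would be 84.1% if both combinations have a hazard ratio of 0.6, but 69.8% if only one does. The documents do not define power this way: SAP Table 2 computes it for one pair.

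A third reply is that SAP Amendment 1 removed type I error control, so no alpha-controlled PFS claim will be made. This does reduce the practical harm. It does not correct the protocol, which still promises strong control, and the SAP gives the sample size calculation as alpha's only remaining use, which is where the wrong word sits. It also means that the entry in SAP 10.1 is evidence of what was intended, not a rule now in force.

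A reader might go further and infer that the trial is underpowered, with about 70% instead of 80%. The documents do not support that. No section adopts a 2.5%/2.5% split, and the test in Protocol 10.4.1 is at 5%. The 70% describes a design that nobody proposed.

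**Conclusion.** The inconsistency is real and confined to the alpha label. The 80% in Protocol 10.1 holds at one-sided 5% for one combination against TG1 (79.7% by direct calculation). The corresponding overall error is about 8.8% when neither combination works and at most 10%, not 5%. The 8.8% assumes approximately normal test statistics and a correlation of 0.5 from equal allocation; the 10% bound needs no assumption about correlation.

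The event target and sample size are sound for the per-comparison design. The range of about 70% to 75.5% at an overall 5% is illustrative only.

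A second mismatch sits behind the first. Protocol 10.3 and 10.6 promise strong control at 10%, while the current SAP has dropped it. Protocol Section 10 says that changes to methods for the primary hypotheses, made after the study starts and before final database lock, will be handled by protocol amendment. The removal appears in SAP 10.2 but not in SAP 10.1, the list of changes to protocol-defined analyses.

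**What to change.** 1. In Protocol 10.1, replace the phrase giving an overall alpha of 5% and favouring one of the combinations with: at a 1-sided alpha of 5% for each comparison of a combination with TG1 (overall 1-sided alpha at most 10% across the two comparisons). Leave the 94 events and the sample size as they are. The illustrative power at an overall 5% need not be printed.

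2. Reconcile Protocol 10.3 and 10.6 with the SAP. Either restore the 10% procedure in the SAP, or amend the protocol to say that the two PFS p-values are nominal and that alpha served only to size the trial. In the second case, word the parenthesis in item 1 as a design calculation rather than a controlled error rate, and list the change in SAP 10.1.

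The cost is one sentence in 10.1 and matching edits to the multiplicity text. The printed overall error rate becomes less favourable, at up to 10% instead of 5%. Enrolment, follow-up and the event target do not change.
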